3.3. Plan for activities, visibility and dissemination

A PhD-dissertation can be completed within three years from project onset; the entire project period is estimated at a maximum of 10 years

A PhD-fellow focusing on research questions a) – c) will be able to complete a dissertation within approximately three years from project onset. However, extensive analyses related to research questions d) – f) are estimated to take longer time, and is also dependent on external funding of additional researchers (PhD and/or postdoctoral positions). Thus, the total project period is estimated at a maximum of 10 years.

Results will be disseminated widely; scientific dissemination is prioritized

Given the seriousness of post-Covid syndrome and the urgent need for scientific knowledge, rapid and continuous dissemination of project results will receive high attention. The target for dissemination is not restricted to the scientific community, but includes a wide range of health-care workers, politicians, policy makers, health care administrators, and the general public.

Several means of dissemination will be exploited, including scientific papers; popular science newspaper articles; giving interviews; meetings with politicians, public health providers and other stakeholders; social media. Dissemination to researchers and the scientific community includes publications in international, peer-reviewed, open access medical journals. The main results will be offered to journals of high impact. Negative findings will also be reported.

3.4. Plan for implementation

Based upon the research results, the Steering Committee will contribute actively to the establishment for clinical guidelines for post-Covid syndrome, in strong collaboration with health administrators,

patients' organizations, and other stakeholders. A Working Group of should be established with the specific task of scrutinizing existing guidelines, revising them, and disseminating the revised guidelines.

4. User involvement

An advisory board of two user representatives is the most important user involvement

For the present project, an advisory board of users will formally established, consisting of a) One representative from the Consumer Advisory Committee at Ahus; and b) One representative from the organization Recovery Norway, consisting of individuals having recovered from PPIS and similar conditions. The advisory board will meet quarterly with the PI; important themes for discussions are results' interpretation and practical impact, ethical issues, considerations regarding further research, and dissemination/implementation strategies.

5. Ethical considerations

Ethics

Participation in the project is based upon informed consent, and thorough information will be provided orally as well as in writing to the participants. All data will be treated and stored without personal identifying information, and in accordance with national directives. Generally, investigational methods are neither harmful nor painful. Approval will be sought from the Regional Committees for Medical and Health Research Ethics. If the intervention is found to be beneficial, participants in the non-intervention group who suffer from a sustained post-Covid syndrome diagnosis will be offered a referral to Kysthospitalet for treatment after completion of the study (Fig. 2).

Gender perspectives

Severe COVID-19 appears to be more common in males than in females. post-infectious complications, however, such as PPIS, are more common among females than males, the ratio being about 3:1. Thus, such complications strongly impact on women's health, but have traditionally received low attention. In this project, possible gender differences will be scrutinized in the analyses.

6. References

Appendix

Overview of inventories

Category	Inventory	Characteristics	References
BACKGROUND/DEMOGRAPHICS			
Household, socioeconomic level		Household members; parents work/education; chronic disease in family	
Smoking, alcohol, drugs		Alcoholic beverages, illicit drugs, smoking; 5-point Likert scale (never to each day)	
SYMPTOMS AND FUNCTIONS			
Fatigue	Chalder Fatigue Scale	11 items; 4-point Likert scale; each item scored 0-3; total sum score range 0 to 33.	Chalder T, Berelowitz G, Pawlikowska T, et al. J Psychosom Res 1993;37:147-53.
Chronic Fatigue Syndrome diagnosis and related symptoms	CDC symptom inventory for CFS	28 items addressing frequency of symptoms on 5-point Likert scale; each item scored 1-5 (never to each day/always).	Wagner D, et al. Popul Health Metr 2005;3:8
post-exertional malaise (PEM)	PEM items from DePaul Symptom Questionnaire	5 items addressing frequency of symptoms on 5 point Likert scale; each item scored 0-4 (never to each day/always). Average, then multiply with 25 to get a 100 point scoring scale.	Bedree H, et al. Fatigue 2019; 7: 166-79
Sleep disturbances	Karolinska sleep questionnaire (KSQ)	12 items addressing frequency of sleep related problems; 6-point Likert scale scored 1 – 6; lower score means more symptoms. Indexes for insomnia, awakening problems, and sleepiness	Akerstedt T, Ingre M, Broman JE, Kecklund G. Chronobiol Int 2008;25:333-48
Pain	Brief Pain Inventory (BPI)	4 items; 10 point Likert scale score 1 - 10 (no pain to worst pain possible)	Klepstad P, et al. J Pain Symptom Manage 2002;24:517-25.
Dyspnoea	Medical Research Council dyspnoea scale	1 item; 5 options (from “breathless during strenuous exercise” to “too breathless to leave the house”).	Bestall JC, et al. Thorax 1999; 54: 581-6.
Depression/Anxiety symptoms	Hospital Anxiety and Depression Symptoms (HADS)	14 items; 4 point Likert scale scored 0 – 3 (8 items with reversed scoring). Indexes for anxiety symptoms and depressive symptoms, also total sum score range 0 to 42.	Zigmond AS, Snaith RP. Acta Psychiatr Scand 1983;67:361-70.
Negative affect	Positive and Negative Affect Schedule (PANAS-SF)	5 items addressing negative affects (ashamed, anxious, nervous, hostile, upset); 5-point Likert scale scored 1-5. Total sum score range 5-25	Thompson ER. J of Cross-Cultural Psychology 2016; 38: 227-42.

Illness perception	Brief Illness Perception Questionnaire	8 items; 10 point Likert scale, scoring 1 – 10.	Broadbent E, et al. J Psychosom Res 2006;60:631-7
Work related self-efficacy	Return-to-work self-efficacy scale (RTWSE-11)	11 items; 6-point Likert scale, scored 1-6 (reverse scoring item 2 and 6). Total sum score range 11 to 66 (higher scores means high work-related self- efficacy).	Shaw WS, Reme SE, Linton SJ, et al. Scand J Work Environ Health 2011; 37: 109-19.
Quality of life	36-Item Short Form Survey (SF-36).	36 items, scored on Likert scales and recoded to achieve 100 point scales (higher score means better health); average score reported. Eight subdomains: Physical functioning; Role limitations due to physical health; Role limitations due to emotional problems; Energy/fatigue; Emotional well-being; Social functioning; Pain; General health	Ware JE, Sherbourne CD. Med Care 1992; 30: 473-83.
Health related quality of life	EuroQoL 5L (EQ-5D-5L)	5 items; 5 point Likert scale, scored 1 to 5. A summary index with a maximum score of 1 (best health status) can be derived from these five dimensions by conversion with a table of scores. In addition: 200 mm VAS scale for assessment on global health status. A score of 100 indicates best health status.	Herdman M, Gudex C, Lloyd A, Janssen MF, Kind P, Parkin D, et al. Quality of Life Research. 2011; 20: 1727-36.
Interoception	Body Vigilance Scale (BVS)	4 items; 11 point Likert scales 0 – 10. Score on item 3 should be divided by 10. Scores on item 4: average among 15 sensations. Total sum score range 0 to 40.	Schmidt NB, et al. J Consult Clin Psychol 1997; 65: 214-20.
Miscellaneous/hypotheses generating		a) 1 item addressing avoidance behavior: “To what degree do you avoid everything that may worsen your symptoms”? b) 1 item addressing school/work absenteeism.	
CONSTITUTIONAL			
Neuroticism	NEO-FFI-30	6 items making up the neuroticism axis; 5-point Likert scale scored 0 – 4. Total sum score range 0 – 24.	Körner A, et al. Psychother Psychosom Med Psych. 2008; 58: 238-245
Worrying tendencies	Penn State Worry Questionnaire (PSWQ)	16 items; 5-point Likert scale scored 1 – 5 (reversed scoring of item 1,3,8,10,11). Total sum score range 16 to 80	Pallesen, S, et al. Scandinavian Journal of Psychology 2006, 47, 281–291
Emotional awareness	Toronto Alexithymia Scale (TAS-20)	7 items making up the index of Difficult identifying feelings. 5-point Likert scale scored 1-5, total sum score range 7 to 49.	Bagby RM, et al.. J Psychosom Res 1994;38:33-40.

Loneliness	UCLA loneliness scale	20 items; 4-point Likert scale scored 1 – 4 (reverse scoring of item 1,5,6,9,10,15,16,19,20). Total sum score from 20 to 80.	Russell, D., et al. Journal of Personality and Social Psychology 1980, 39(3), 472–480
Self-efficacy	General Self-Efficacy Scale, short form	6 items; 4-point Likert scale scored 1 – 4. Total sum score from 6 to 24.	Romppel M, et al. Psychosoc Med 2013; 10: Doc01.

## 1. DESIGN

### Design overview

The proposed study is a 2-arm pragmatic randomised controlled trial (RCT) in which 310 patients who suffer from post-Covid syndrome are randomised to either a short-time outpatient-based rehabilitation program (the intervention) or care as usual in a 1:1 ratio (Fig. 1). Assessments will take place immediately before randomisation (T0), after intervention or care as usual (T1), and 12 months after T0 (T2). Of note, the timing of T1 will vary in the intervention group, due to the individualized therapy approach (cf. below); T1 in the non-intervention group will be matched accordingly. Patients will be recruited from General Practitioners (GP's) as well as social media and self-referral to the involved institutions, and included based upon the criteria listed in Table 1.

---

**Table 1. Criteria for inclusion and exclusion**

---

Inclusion criteria	Exclusion criteria
Fulfills pragmatic diagnostic criteria of idiopathic post-Covid syndrome: 
 
• Confirmed acute Covid-19 by a positive PCR or self-test for SARS-CoV-2.
 
• Persistent symptoms at least 3 months following acute Covid-19 without symptom-free interval.
 
• Functional disability to an extent that interrupts all or a majority of normal activities (such as work/school attendance, physical exercise, social activities, etc.)
 
	Other chronic illnesses or demanding life situations that might explain persistent symptoms and disability
Age ≥ 16 years	Sustained organ damage (lung, heart, brain) following acute, serious Covid-19
Lives in one of the following Norwegian counties: Oslo, Viken, Innlandet, Vestfold og Telemark, Agder	Bedridden
Informed consent to participation	Insufficient command of Norwegian language

---

### Randomisation and blinding

Patients eligible for the present study are randomized to either intervention or care as usual in a 1:1 probability by a computer-based routine for block randomization; block size will vary randomly between 4 and 6. Allocation will be stratified by severity of illness during the acute stage of Covid-19, operationalized as (1) no admission to hospital, (2) admission to hospital. Allocation concealment will be ensured using sequentially numbered, opaque, sealed envelopes. It is not possible to blind for treatment due to the nature of the intervention. However, during endpoint-evaluation, the responsible researchers will be blinded for group allocation.

### Effect monitoring

Effect monitoring is primarily based on patient reported outcome measures (PROM), applying a web-based questionnaire composed of several validated instruments. The questionnaire will be distributed to the participants at T0, T1 and T2. It will chart clinical symptoms as well as background, psychological and social variables, and will be used for subgrouping according to case definitions of post-COVID-19 syndrome and post-infective fatigue syndrome. The SF-36 subscale Physical Functioning (SF-36-PFS) score at T1 will serve as the **primary endpoint**.

Secondary endpoints include score of PROM inventories at T1 and T2, such as:

- *The Chalder Fatigue Questionnaire (CFQ)* charts subjective experience of physical and mental fatigue. In this study, the CFQ total linear score (i.e. the sum across all 11 items, each item scored on a zero to three Likert scale) will be applied. Furthermore, fatigue

caseness is defined as a CFQ total dichotomous score of 4 or higher (each item scored 0-0-1-1).

- *The Hospital Anxiety and Depression Scale (HADS)* is a validated questionnaire for charting symptoms of depression and anxiety. It consists of 14 items rated zero to three on Likert scales, allowing computation of sub-scores for depression and anxiety symptoms. In the present study, these sub-scores as well as total sum score will be applied.
- *Adverse effects*: A self-invented questionnaire will address possible adverse effect related to the intervention.

Cf. protocol with appendix for at detailed overview of inventories. In addition, employment status, usage of social security-systems (i.e. short and long-term sick leave), and usage of health care services (i.e. the number of GP and specialist contacts, hospitalisations, medications, usage of rehabilitation services, etc.) will be charted through register linkage (cf. below) as well as questionnaires to the study participants.

Also, recovery from post-infective fatigue syndrome will serve as an endpoint. The appendix of the present statistical analysis plan provides an operationalization of post-infective fatigue syndrome according to the Fukuda-definition within the context of the present study.

[figure not shown]

Figure 1. Overview of study design

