1.1 Needs description

The present study addresses urgent needs for the health care services as well as the scientific community

- *Patient treatment.* This project directly addresses a strong need to develop effective treatment strategies for a large patient group suffering from post-Covid syndrome disability. Thus, it significantly improve health care services. Of note, the pragmatic approach ensures strong external validity and generalizability of the results.
- *Relevance and benefit to society.* This project addresses a highly challenging health problem nationally and internationally, which may have substantial negative impact upon employment issues, social security systems, family networks etc.
- *Scientific relevance.* The project addresses a prominent knowledge gap. Also, as the intervention builds upon a specific pathophysiological model, the study results will provide increased insight in disease mechanisms, and may eventually foster similar studies in PPIS following other infections.

2. Hypotheses, aims and objectives

We hypothesise that a short-time outpatient-based rehabilitation program will be beneficial as compared to usual care in post-Covid syndrome

The aim of the present study is to assess the efficacy of a short-time outpatient-based rehabilitation program (the intervention) as compared to usual care (non-intervention) in post-Covid syndrome. The objectives are:

- a) To determine the effect on physical functioning immediately after completion of the intervention. We hypothesises better physical functioning in the intervention group than in the non-intervention group.
- b) To determine the effect on other post-Covid syndrome symptoms (such as fatigue, cognitive difficulties, dyspnoea, pain, sleeping problems) and quality of life (QoL) immediately after completion of the intervention. We hypothesise a beneficial effect of the intervention across all these domains.
- c) To determine adverse effects of the intervention. We hypothesis no differences in the frequency nor seriousness of adverse effects in the intervention group as compared to the non-intervention group.
- d) To determine the effect of the intervention on a long-term basis. We hypothesise that a beneficial effect of the intervention is sustained six months after its delivery.

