Variables will be reported with parametric or non-parametric descriptive statistics, eventually frequency tabulation, as appropriate. General linear models (ANCOVA) will be used for analyses of treatment effect; the baseline values of each efficacy endpoint will be included as covariates. For each statistical analysis, the net intervention effect (the mean change in the intervention group minus the mean change in the usual care group) will be calculated from the parameters of the fitted general linear model and reported with 95 % confidence interval. All statistical tests will be carried out two-sided. A p-value ≤ 0.05 is considered statistically significant. Safety data will be summarized descriptively through appropriate data tabulations and descriptive statistics. No interim analysis will be carried out. A statistical analysis plan will be developed.

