### 4. STATISTICAL METHODS

#### **General considerations**

Continuous variables will be reported with parametric (mean/standard deviation) or non-parametric (median, quartiles) descriptive statistics, depending on the distribution.

Ordinal/nominal variables will be reported as frequency tabulation. All statistical tests will be carried out two-sided. A p-value  $\leq 0.05$  is considered statistically significant.

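### Secondary endpoints are listed by example and every test is called significant at unadjusted p ≤ 0.05, so which scores count can be settled after the data are seen and false positives are not controlled

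*SAP*

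**What the plan says.** The primary endpoint is fixed. SAP, Effect monitoring: "The SF-36 subscale Physical Functioning (SF-36-PFS) score at T1 will serve as the" primary endpoint.

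The secondary endpoints are not. The same section says "Secondary endpoints include score of PROM inventories at T1 and T2, such as" and then describes three items:
- CFQ: "the CFQ total linear score (i.e. the sum across all 11 items, each item scored on a zero to three Likert scale) will be applied", and a dichotomous caseness definition is added.
- HADS: "these sub-scores as well as total sum score will be applied".
- A questionnaire on adverse effects.

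It then refers to the protocol appendix for the inventories. It also adds recovery from post-infective fatigue syndrome (PIFS) as an endpoint, without saying whether this ranks as secondary.

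The threshold is general. Protocol section 3.1, Statistical analyses: "A p-value ≤ 0.05 is considered statistically significant". The SAP repeats this under General considerations, with "All statistical tests will be carried out two-sided". SAP, Analyses of intervention effect, sets a null hypothesis of no difference in the efficacy variables and asks for an estimate with a 95% confidence interval from each analysis. Safety data are descriptive only.

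Protocol section 2, objective b, on symptoms and quality of life after the intervention: "We hypothesise a beneficial effect of the intervention across all these domains".

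**The concern.** Two gaps combine. First, the words of example leave open which appendix inventories are endpoints, and which score from each. The appendix gives eight SF-36 subdomains and also mentions an average score, three indexes for the sleep questionnaire, and both an index and a visual analogue scale for EQ-5D-5L. A reader of the final report could not tell from the SAP whether a given scale had been designated in advance as an endpoint.

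Second, one threshold is applied to every test, with nothing to limit how often it is crossed by chance. Objective b is worded as a hypothesis of benefit, and objective d extends it to the long term, so an isolated significant scale could be read as a finding. Section 3.4 of the protocol plans to carry the results into clinical guidelines, so that reading would have consequences.

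**Working it through.** **The plan's own figures.** The documents give no error rate for the secondary family, so there is none to reproduce. The one related figure is power for the primary endpoint: 310 × 0.8 = 248, or 124 per arm. With difference 10, SD 25 and two-sided 0.05, power is Φ(10 / (25·√(2/124)) − 1.96) = 88%, within 2 points of the stated 90%. It rests on a single test at 0.05, which the secondary endpoints do not affect.

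**Number of tests.**
- Named set (SAP, Effect monitoring): CFQ 2 (linear, caseness) + HADS 3 (two sub-scores, total) = 5 scores. At T1 and T2: 5 × 2 = 10.
- Symptom and function set (counted here from the protocol appendix): CFQ 2, CDC inventory 1, post-exertional malaise 1, sleep 3, pain 1, dyspnoea 1, HADS 3, negative affect 1, illness perception 1, return-to-work self-efficacy 1, SF-36 other than physical functioning 7, EQ-5D-5L 2, body vigilance 1 = 25. At two times: 50.
- Wider count: 25 + 2 single items + PIFS recovery = 28; 28 × 2 = 56; plus SF-36-PFS at T2 = 57.

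The constitutional scales, register outcomes, per-protocol repeats and subgroup tests are left out.

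**Formulas, with no true effect on any secondary endpoint.** For k independent tests:
- any false positive = 1 − 0.95^k
- false benefit only = 1 − 0.975^k

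For k = 10: 1 − 0.95^10 = 0.401 and 1 − 0.975^10 = 0.224. For k = 57: 0.946 and 0.764.

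For a common correlation ρ, write each test statistic as √ρ·X + √(1−ρ)·e, with X and e standard normal and c = 1.96. Then:
- any = 1 − ∫ [Φ((c − √ρ x)/√(1−ρ)) − Φ((−c − √ρ x)/√(1−ρ))]^k φ(x) dx
- benefit only = 1 − ∫ [Φ((c − √ρ x)/√(1−ρ))]^k φ(x) dx

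The documents give no correlation, so ρ from 0 to 0.7 is an assumption.

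| Tests | Error | ρ = 0 | 0.3 | 0.5 | 0.7 |
|---|---|---|---|---|---|
| 10 | any | 40% | 35% | 29% | 21% |
| 10 | benefit only | 22% | 18% | 14% | 11% |
| 50 | any | 92% | 81% | 62% | 40% |
| 50 | benefit only | 72% | 45% | 32% | 20% |
| 57 | any | 95% | 84% | 65% | 42% |
| 57 | benefit only | 76% | 47% | 33% | 21% |

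The expected number of false positives does not depend on ρ: 0.05 × 10 = 0.5, 0.05 × 50 = 2.5 and 0.05 × 57 = 2.85.

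**The case against.** The case for the plan has several parts.

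- **The list is finite.** The protocol appendix names the inventories and in most cases their scoring. This stands: the freedom is selection within that list, not invention of new scales.
- **The larger counts are a reviewer's construction.** The SAP does not say that every appendix score is an endpoint. The 57 includes two items that the appendix itself marks as hypothesis-generating, and an inventory listed under diagnosis. This stands, and is why the ten-test figure is given first. It also illustrates the gap, because the SAP gives no count to use instead.
- **The scores overlap.** The HADS total is the sum of its sub-scores, and both CFQ scores use the same 11 items. This stands: the independence column is an upper end, not an expectation.
- **There are safeguards.** Effects are reported with confidence intervals, the protocol promises to report negative findings, and researchers are blinded to allocation during endpoint evaluation. These help, but none fixes which scores are endpoints or says how their p-values are to be read.
- **Objective b concerns all domains,** so one significant scale would not confirm it. This is a fair reading, but the significance rule operates score by score.

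A reader might infer that a false claim of benefit is likely. The figures do not support that. False benefit exceeds 50% only when about 50 tests are nearly independent. At a correlation of 0.5 it is 33% for 57 tests and 14% for the ten named. A reader might also tie the point to the lack of treatment blinding. That is a question of bias in patient-reported outcomes; it does not enter this calculation, and no multiplicity adjustment would correct it.

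**Conclusion.** The point holds for the secondary endpoints only. Their list is not closed, and every test carries the same unadjusted threshold with no exploratory label in the text supplied; a few parts of both documents were not available to check. Even the smallest case, ten named tests at correlation 0.7, gives a 21% chance of some false positive, about four times the nominal 5%. The upper ends, 95% for any false positive and 76% for a false benefit, need 57 independent tests and should not be quoted alone. All figures assume that no secondary effect is real and that the correlation is common to all pairs. The gap in the list needs no probability model. The primary analysis and its 5% error are unaffected, so this is a cheap improvement and not a threat to the main conclusion.

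**What to change.** Before the unblinded analysis, amend the SAP as follows.

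1. Replace the words of example with a closed list of secondary scores, each with its name, scoring and time point. State the rank of PIFS recovery.
2. Keep the label of statistical significance for the primary endpoint and, if wanted, a short set that includes SF-36-PFS at T2. Test that set with Holm, and only if the primary is significant. Name the set score by score: choosing one score per domain of objective b would not close it, because that objective also lists its domains by example.
3. Report all other scores as estimates with 95% confidence intervals, described as exploratory and without a significance label. The SAP already requires these intervals.

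The set should be short because adjustment is costly over a long one: a Bonferroni threshold is 0.05/10 = 0.005 for ten tests and 0.05/50 = 0.001 for fifty. If the sponsor wants no confirmatory secondary claims, labelling all secondary results exploratory would also meet the concern about significance claims; the closed list would still be needed.

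The cost is SAP wording. No data, sample size or primary analysis changes. The downside is that some secondary results can no longer be called significant.
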